The primary objective of this study is to quantify the hyperpigmentation response after 1927nm non-ablative fractionated laser therapy in subjects with Fitzpatrick Skin Phototypes V and VI and explore an effective, adjunctive pre- and post-procedural topical regimen to prevent iatrogenic dyspigmentation or scarring in this population.

We will explore this question with a non-blinded, observational study at a single center.

Clinical Study Design

Overview of Clinical Study

This is a single-site, prospective observational, non-randomized, non-controlled pilot study being conducted at the University of Texas Southwestern Medical Center at Dallas in the Department of Plastic Surgery. The study is designed to follow changes in hyperpigmentation in approximately 20 qualified and consenting subjects receiving f1927 hyperpigmentation standard care treatment using VISIA and/or VISIA-CR. The Principal Investigators (PIs) have been selected based on their expertise, qualifications, subject access, prior clinical research, facilities, and interest in this field of research. Subjects will be recruited through IRB-approved advertisements or identified by [name] at the University of Texas Southwestern Medical Center. Subjects will be numbered sequentially in the order in which they initially qualify for entry into the study. Subjects who continue the study from Part 1 will retain their subject number through Part 2. Any new subjects recruited for Part 2 will be numbered sequentially in the order they qualify for entry into the study.

Part 1:

Study doctors will explain and prescribe subjects a standard of care topical regimen 4-6 weeks prior to f1927 treatments.

Part 2:

Subjects will be asked to complete a month-long washout period of all topical regimens prior to f1927 treatments. Following each treatment subjects will be asked to apply Clobetasol twice a day for four days and apply ice to the treated areas four times a day.

Clinical Treatment and Assessments

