Participating subjects will receive treatment using an FDA-approved f1927 laser, currently considered a standard of care treatment for melasma and hyperpigmentation in Fitzpatrick Skin Phototypes I-VI. Subjects will undergo treatments over the entire face. Subjects' response to effects of the f1927 treatment will be quantified based on evaluation of standard and clinical photography and H2 3D Imaging System images taken pre- and post-procedure. These photos will be identifiable full-face photos, and subjects will be adequately informed and consent of such. In addition to the two standard care photographic assessments, subjects will also have photos taken using the VISIA and/or VISIA-CR (Canfield Scientific, Fairfield, NJ). A quantitative assessment of the effects of treatment will be performed using VISIA and/or VISIA-CR at 1-month and 3-months post-treatments. Additional assessment will be provided by use of the Skin Hyperpigmentation Index (<https://shi.skinimageanalysis.com/> - Inselspital, Freiburgstrasse, Switzerland) [12-15] a web-based software used to quantify hyperpigmentation. Changes in the Skin Hyperpigmentation Index over time will be used to objectively report on subjects' treatment response.

From these procedures, the improvement in diffuse pigmentary changes can be evaluated in comparison to pre-treatment assessments.

Primary Endpoints

1. Quantifying Improvement in overall facial hyperpigmentation in response to laser treatment, by measuring pigmentation at baseline and follow-up visits post-treatment using the VISIA and/or VISIA-CR
2. Changes in Skin Hyperpigmentation Index (SHI) Scores from Baseline to post-treatment visits..

Secondary Endpoints

1. Monitoring incidence, severity, and relatedness of adverse events throughout the study
2. Monitoring the efficacy of pre- and post-treatment regimens with tretinoin and hydroquinone
3. Monitor the efficacy of the pre- and post-treatments with Clobetasol and ice.

Standard of Care Treatment Device

Proprietary Name	Device Description	Regulatory Information
Sciton MOXI	Aesthetic device that utilizes a fractionated laser to initiate resurfacing for the treatment of dyspigmentation and healing of photoaged skin.	Class II 510(K) Number: N/A Regulation Number: 878.4810

Study Population, Screening, and Enrollment

Study Population

The study population in question includes patients ages 18-75 with Fitzpatrick Skin Phototypes V and VI.

Subject Enrollment

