Appropriate post-treatment care instructions will be provided as deemed appropriate by the Investigator or study staff. Post-treatment assessment will be performed. Subjects will be instructed that blistering, bleeding, oozing, strong pain, swelling persisting for more than 72 hours, or signs of infection (e.g., pus, drainage, fever) are cause for immediate concern and they should contact the investigator and/or his designee, to be evaluated. Expected downtime is minimal after treatment, typically lasting 0-3 days.

These visits will take approximately 1 hour.

Visit 4 and Visit 5: Follow-Up Visits 1 and 2

Day 90, Day 150

At a minimum, all subjects will return for follow-up visits at 1 month (\pm 7 days) and 3 months (\pm 7 days) after treatment.

The following activities will be performed on all study subjects during the follow-up visits:

7. The physician or study staff will ask subjects if they have experienced any changes in their health since the previous visit. Changes will be recorded accordingly. If an adverse event (AE) is reported than the Investigator will be informed, and an AE form will be completed. This is standard of care.
8. Subjects will acclimate to ambient temperature and humidity conditions for 15 minutes prior to any procedures being done. This is standard of care.
9. The physician or study staff will perform an examination of the skin in the treatment area. This is standard of care.
10. Obtain post-treatment close-range clinical photography as described in section entitled, "Assessments", for research purposes.
11. Obtain post-treatment photographs using the Vectra H2 3D Imaging System, as described in section entitled, "Assessments", for research purposes
12. Obtain post-treatment photographs VISIA and/or VISIA-CR as described in section entitled, "Assessments", for research purposes.

These visits will take about 30 minutes.

Assessments

Photography Procedures

Nikon D7200 (Standard of Care)

Standard and close-range of the face will be utilized for evaluation of pigmentation. These photographs will be taken utilizing the Nikon D7200 at Baseline (Screening Visit), 1-month post-treatment and 3-months post-treatment.

Vectra H2 3D Imaging System (Standard of Care)

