Subjects will be instructed to adopt neutral, non-smiling expressions for each photograph. Images will be taken of each applicable subject with diffuse pigmentation of the face using the Vectra H2 3D Imaging System at Baseline, 1-month post-treatment and 3-months post-treatment. Each subject will have a total of 3 photos taken (right side, left side and center view).

VISIA and/or VISIA-CR (Research Purposes)

Subjects will be instructed to adopt neutral, non-smiling expressions with their eyes gently closed for each photograph. Images will be taken of each applicable subject using the VISIA and/or VISIA-CR at Baseline, 1-month post-treatment and 3-months post-treatment. Subjects will be carefully positioned for each photograph, directly facing the camera for the center view, and turned at a 45° angle for right and left side views. The scan is objectively able to quantify brown spots for assessment and comparison.

Hyperpigmentation Assessment

Skin Hyperpigmentation Index (SHI) (Research Purposes)

The SHI will be calculated using de-identified, cropped images from patient's unaffected skin and patient's hyperpigmented lesions. Images uploaded will be selected from the clinical or lab-based photography the patient has taken at their screening/baseline visit and their 1-month and 3-month follow-up visits. Care will be taken to compare lesions using the same lighting and angles to reduce confounders. The software is able to calculate the relative contributions of pigmentation of each pixel to create a score, and a coefficient is then derived from comparing Pigmentation Scores of the Area with hyperpigmentation versus the Reference Point. This will be used to quantify the change in pigmentation between treatments.

Statistical Methods of Analysis

The per-protocol (PP) population will be the primary population for all statistical analyses. The PP population will include all subjects who received treatment and completed the study in general accordance with the protocol. Only the data of completing subjects will be analyzed.

This study will include descriptive statistics and change from baseline analysis.

The primary outcome of effectiveness will be a paired comparison of baseline to all applicable post-baseline time points for hyperpigmentation and melasma severity using data obtained from VISIA and/or VISIA-CR and the Skin Hyperpigmentation Index results.

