A descriptive statistical summary will be provided via the VISIA and/or VISIA-CR. The descriptive statistical summary includes the number of observations (n), mean, median, and standard deviation (SD), minimum (MIN) and maximum (MAX) values at all applicable time points.

A Skin Hyperpigmentation Index is derived automatically using the SHI plug-in. The SHI ranges from 1 (no hyperpigmentation) to 4 (maximum hyperpigmentation) and is a ratio between the Pigmentation Scores of Areas with Hyperpigmentation versus Pigmentation Score of the Reference Point.

The following will be calculated and reported for each evaluation parameter at the applicable post-baseline time point(s):

$$\text{Percent Mean Change from Baseline} = \frac{(\text{Visit Mean Score} - \text{Baseline Mean Score}) \times 100}{\text{Baseline Mean Score}}$$

For each new measurement set we will conduct a repeated measures of analysis of variance (ANOVA) to detect difference between sample distributions. If differences are detected, we will subsequently evaluate specific pairwise comparisons among the post-treatment visit times using a paired T-test or Wilcoxon signed-rank tests. All statistical tests will have a significance level $\alpha=0.05$ (i.e., $p<0.05$). P-values will be reported to 3 decimal places (0.000).

Potential Risks

Standard of Care Risks

Pre-Treatment: Hydroquinone (Rare)

Hydroquinone is a known and effective treatment for hyperpigmentation disorders and is particularly considered to be the standard of care for dermatologic treatment of unwanted hyperpigmentation. Reported adverse effects of hydroquinone administration are uncommon and include short-term cutaneous side effects like irritant contact dermatitis or, with excessive or long-term use or misuse, exogenous ochronosis. Additionally reported side effects include abnormal skin re-pigmentation in continually sun-exposed areas, or trimethylaminuria with chronic use.

Pre-Treatment: Topical Tretinoin (Rare)

Side effects of topical tretinoin are rare and include stinging of the skin, local dryness, hypopigmentation, application site reactions like erythema, irritation, or exfoliation, or, most rare, contact dermatitis or long-term skin changes.

Treatment: Non-Ablative Laser Facial Resurfacing (Rare)

Blistering, burning, scaling and infection (Rare)

A crust, blister or superficial wound can occur in the treatment area. The risk of infection will be minimized by proper wound care.

Bruising (Rare)

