The risks of photography and imaging are the same for all three imaging modalities used: close-range clinical photography (Nikon D7200), 3D Photography (Vectra H2), and the VISIA and/or VISIA-CR. Photographs include a risk of identification, as these will be full face photos. Privacy will be protected to the greatest extent possible. Photos will only be identified by unique subject identification number that contains no personal identifying information. All photos will be stored on a password secure drive, with only access by research personnel. For research purposes, photos may be used in scientific publications.

Adverse Events

At each visit, a member of the research team will question the subject about adverse events using an open-ended question. If a potential adverse event is reported by the subject or identified during examination, directed questioning and examination will be performed when appropriate. At this time, the following will be performed:

1. Obtain a complete history of the event in question as well as conduct an examination of the subject and determine if the reported event qualifies as an Adverse Event (AE). If the event is determined to be an AE, an AE case report form and Event Follow-up (EF) visit case report form must be completed. One AE case report form should be used to track the history of an individual AE throughout the period of the study.
2. Collect an updated medical and surgical history along with recording of concomitant medications or treatments.
3. Take photographs of the subject with attention to the area in question.
4. Render treatment for the event, if any, as determined by the medical judgement of the Investigator.

Photographs will be taken to document any AEs if possible.

For the duration of the study, medical assistance will be provided to the subject for study-related problems at no expense, if in the opinion of the Investigator, the reaction was caused by MOXI treatments. Should a subject choose to seek their own medical treatment, no reimbursement will be offered.

When an AE persists at the end of the study, the Investigator will ensure a follow-up of the subject until the Investigator believes that the event is satisfactorily resolved.

Subject Safety and Data Monitoring

Research Standards and Good Clinical Practice

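### The plan does not fix which camera, lesion and reference crops feed the Skin Hyperpigmentation Index, so favourable selection could create apparent improvement on a primary endpoint

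*Combined protocol and SAP*

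**What the plan says.** The Primary Endpoints section lists two endpoints. The second is "Changes in Skin Hyperpigmentation Index (SHI) Scores from Baseline to post-treatment visits". Statistical Methods of Analysis puts SHI, with the VISIA data, into the paired comparison of baseline with post-baseline visits.

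The SHI section under Hyperpigmentation Assessment describes the input: "The SHI will be calculated using de-identified, cropped images from patient's unaffected skin and patient's hyperpigmented lesions". On the source it says "Images uploaded will be selected from the clinical or lab-based photography the patient has taken at their screening/baseline visit", and likewise for the 1-month and 3-month visits. The section on photography risks names three systems: "close-range clinical photography (Nikon D7200), 3D Photography (Vectra H2), and the VISIA and/or VISIA-CR". Vectra and VISIA each supply right, left and center views.

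Two statements limit discretion. The SHI section says "Care will be taken to compare lesions using the same lighting and angles to reduce confounders", and Statistical Methods says "A Skin Hyperpigmentation Index is derived automatically using the SHI plug-in". On blinding, Purpose and Objective says "We will explore this question with a non-blinded, observational study at a single center".

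The baseline image set is not unique. Photography Procedures schedules the standard photographs "at Baseline (Screening Visit), 1-month post-treatment and 3-months post-treatment". The treatment-visit descriptions for both Parts call for a further full image set before the first laser session. In Part 1 the pre-treatment topical regimen falls between those two sets.

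**The concern.** The scoring is automatic, but its input is not. SHI is a ratio of the score in a lesion crop to the score in a crop of the subject's own unaffected skin. Whoever supplies the files chooses a photograph, a lesion area and a reference area for each visit, and each choice moves the ratio. Nothing in the plan ties the choice at Day 90 or Day 150 to the choice at baseline beyond the intention to match lighting and angle.

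A mild, unintended preference for the clearest lesion at baseline is enough to bias the change towards improvement. There is no control arm in which the same bias would appear and cancel. At stake is whether a fall in SHI can be read as a treatment response.

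**Working it through.** The plan gives no power calculation and no SHI repeatability, so there is no stated figure to reproduce. The check asks how often selection alone would give a significant improvement when nothing has changed.

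**Inputs from the documents.** About 20 subjects (Overview of Clinical Study); paired comparison at alpha 0.05 (Statistical Methods), taken as two-sided because sidedness is not stated. The chance level in the direction of improvement is therefore 0.05 / 2 = 2.5%.

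**Assumptions not in the documents.**
- k = 2 or 3 candidate images per visit, with independent image errors of SD 1.
- The darkest candidate is taken at baseline and an arbitrary one at follow-up.
- This happens in a share q of subjects: 25%, 50% or 100%.
- Variation common to all images at a visit has variance r times the image-error variance: r = 0, 1 or 3.

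**Model.** For subject i, change = (F + V_F) - (max of B_1..B_k + V_B). F and B are image errors; V_F and V_B are the shared visit terms.

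**Bias if all subjects are affected.**
- k = 2: expected maximum = 1/√π = 0.564, so the mean change is about -0.56 image-error SD.
- k = 3: expected maximum = 3/(2√π) = 0.846, so the mean change is about -0.85 image-error SD.

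**Hand check for k = 3, q = 100%.** The variance of the maximum of three is 0.5595, so the variance of the change is 1 + 0.5595 + 2r. The expected t is about 0.846 × √20 / SD:
- r = 0: SD = √1.5595 = 1.249, expected t = 3.03.
- r = 1: SD = √3.5595 = 1.887, expected t = 2.00.
- r = 3: SD = √7.5595 = 2.749, expected t = 1.38.

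Against the critical value of 2.093 on 19 degrees of freedom, these agree with the simulated 82%, 48% and 26%.

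**Simulated chance of a significant false improvement** (n = 20, paired t-test, 40,000 runs):

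| Candidates | Share affected | r = 0 | r = 1 | r = 3 |
|---|---|---|---|---|
| 2 | 25% | 6% | 5% | 4% |
| 2 | 50% | 14% | 9% | 6% |
| 2 | 100% | 45% | 23% | 14% |
| 3 | 25% | 10% | 7% | 5% |
| 3 | 50% | 25% | 15% | 9% |
| 3 | 100% | 82% | 48% | 26% |

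**Does matching the follow-up image help?** If the darkest baseline crop is kept and the same camera and crop are used at follow-up, the rates with r = 0 and all subjects affected are 44.8% (k = 2) and 82.1% (k = 3). This is unchanged within simulation error, because the bias comes from picking an extreme baseline and regression to the mean does the rest. Keeping the better of two fully matched pairs gives 9.3%, 24.8% and 83.3% for a quarter, half and all of the subjects.

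**One prespecified image and crop (k = 1).** The false-improvement rate returns to 2.3-2.7% and the bias to zero.

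**Fewer completers.** Only completers are analysed. With n = 15, k = 3 and r = 0, the rates are 8.0%, 19.7% and 69.1%.

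**The case against.** The plan has real safeguards. Matching lighting and angle, read naturally, discourages pairing a baseline from one camera with a follow-up from another. A ratio to the subject's own skin should offset some exposure differences when both crops come from one image. Scoring is automatic. The other primary endpoint, from VISIA, uses set views with no lesion cropping described, so a spurious SHI result would have a companion measure. This is also a pilot. All of that stands and narrows the problem, but none of it fixes the lesion, the reference site or the camera. De-identifying the crops hides the person, not the visit.

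A reader might infer several stronger things that the documents do not support:
- **That unblinded staff pick the images after follow-up is complete, knowing the visit.** The selector, the timing and the selector's knowledge of visit are not stated. Non-blinded describes the study as a whole. The plan permits such selection and does not prevent it, but does not say it happens. No misconduct is implied.
- **That 82% is the expected error rate.** It needs the darkest of three images with independent errors in every subject. With shared visit-level variance it falls to 48% or 26%, and with a quarter of subjects affected it is 5-10%.
- **That the two primary endpoints are co-primary in the strict sense.** The documents list two and do not use that term.

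The simulation covers one paired t-test and not the preceding repeated-measures ANOVA. The bias is in image-error SDs and cannot be converted to points on the 1-4 SHI scale.

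**Conclusion.** The concern holds in a limited form. Selection of image, lesion and reference crop for a primary endpoint is left open and no masking to visit is described. The existing safeguards reduce the room for selection without closing it.

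The illustrative false-improvement rate is about 4-10%, 6-25% or 14-82% when a quarter, half or all of the subjects are affected, against 2.5% nominal. The lower end of each range has 2 candidates and shared variance three times the image-error variance; the upper end has 3 candidates and no shared variance. Every one of these settings is an assumption. If selection is favourable, the direction of the bias does not depend on them, but its size does. The change should be made and is proportionate for a pilot.

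**What to change.** 1. Name one camera system and one view for all SHI images, and state which pre-treatment image set is the baseline: screening or immediately before the first laser session.
2. Before the first laser session, choose the index lesion(s) and the reference area by a stated rule that does not depend on the baseline SHI score, for example all lesions in predefined facial zones or a fixed anatomical site. Mark them, and re-crop the same landmarks at Day 90 and Day 150. A rule that picked the darkest lesion would leave regression to the mean in place.
3. Have existing staff code and shuffle the images before cropping, so that the person placing the crops does not know the visit. Masking only the upload step would achieve little, since the software is automatic and the judgement lies in the cropping.

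The cost is protocol wording and minor file handling, with no new visit or equipment. The downside is that a subject whose image from the named camera is unusable has no SHI value at that visit.

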19. Individuals who are pregnant or nursing or those planning on becoming pregnant during the study according to self-report.
20. Immunocompromised individuals or those currently using immunosuppressive medications and/or radiation.
21. Individuals with uncontrolled disease such as asthma, diabetes, hyperthyroidism, medically significant hypertension, or hypothyroidism. Those with multiple health conditions may still be excluded from participation even if conditions are controlled.
22. Individuals with any planned surgeries, overnight hospitalization, and/or invasive medical procedures planned during the study.
23. Individuals who, in the Investigator's opinion, have a history of poor cooperation, unreliability or noncompliance with medical treatment.
24. Individuals who are unable to understand instructions or give informed consent
25. Individuals who have physical or psychological conditions which, in the opinion of the Investigator, makes them unable to complete the study per protocol (e.g., not likely to avoid other cosmetic treatments to area; not likely to stay in study for entire duration due to other commitments; or those with concomitant conditions that may develop symptoms that might confuse or confound study treatments or assessments).
26. Individual who are using hydroquinone and tretinoin (4 wk wash out period necessary before treatment).

Subject Instructions

Part 1:

At subject's initial Screening visits, subjects will discuss the adjunctive topical regimen with their provider and have these prescriptions sent to a pharmacy of their choice. The adjunctive regimen is standard care and is outlined below:

Pre-treatment

1. 4-6 weeks of 4% Hydroquinone cream applied twice daily to entire face
2. 4 weeks of Tretinoin 0.1% cream applied nightly to entire face
3. Judicious application of physical sunscreen of \geq SPF 30 at least 15 minutes before sun exposure with reapplication after water exposure.

Post-treatment

Patient should resume use of topical hydroquinone and retinol regimen the same evening as their last laser treatment, as enumerated below:

1. 4 weeks of 4% Hydroquinone cream applied twice daily to entire face
2. 4 weeks of Tretinoin 0.1% cream applied nightly to entire face
3. Judicious application of physical sunscreen of \geq SPF 30 at least 15 minutes before sun exposure with reapplication after water exposure.

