2. Assign a screening number to candidate subjects that sign the initial paperwork.
3. Collect a brief medical history including current medications, skin type, allergies, major conditions, or illnesses, etc. and assess if subjects meet eligibility criteria.
4. For those that pass eligibility requirements and are females of childbearing potential, perform a urine pregnancy test. If the test is negative or candidate is male, the subject will be enrolled in the study and assigned a subject number.
5. Obtain close-range standard photography as described in section entitled, Assessments. This is standard of care.
6. Obtain photographs and measurements using the Vectra H2 3D Imaging System and VISIA and/or VISIA-CR System as described in section entitled, "Assessment", for research purposes.
7. Study doctors will call in prescriptions to the subjects preferred pharmacy. This is standard of care.

This visit will take 30-45 minutes.

Visit 2, Visit 3, and Visit 4: Treatment Visits 1-3

Day 0, Day 30, Day 60

A member of the study team will record concomitant medications and will ask subjects if they have experienced any changes in their health since the previous visit. If an adverse event (AE) is reported than the Investigator will be informed, and an AE log will be completed/updated for PI review.

The following activities will be completed before the treatment:

1. The physician or study staff will ask subjects if they have experienced any changes in their health since the previous visit. Changes will be recorded accordingly. If an adverse event (AE) is reported than the Investigator will be informed, and an AE form will be completed.
2. Subjects will acclimate to ambient temperature and humidity conditions for 15 minutes prior to any procedures being done.
3. Obtain close-range standard photography as described in section entitled, "Assessments". This is standard of care. This will only be completed before their first treatment.

4. Obtain photographs and measurements using the Vectra H2 3D Imaging System and VISIA and/or VISIA-CR as described in section entitled, "Assessment", for research purposes. This will only be completed before their first treatment.

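### Baseline is tied to Screening for SHI and the Nikon photographs and left undefined for VISIA and in the statistics section; the Day 0 pre-laser images have no analysis role, so in Part 1 change from Screening includes the topical run-in

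*Combined protocol and SAP*

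**What the plan says.** The plan speaks of baseline in several places, and not in the same way.

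- **SHI** (Hyperpigmentation Assessment): images come from photography "the patient has taken at their screening/baseline visit and their 1-month and 3-month follow-up visits". Baseline and Screening are treated as one visit.
- **Nikon photographs** (Photography Procedures): taken with the "Nikon D7200 at Baseline (Screening Visit), 1-month post-treatment and 3-months post-treatment".
- **VISIA** (Photography Procedures): images are taken "using the VISIA and/or VISIA-CR at Baseline, 1-month post-treatment and 3-months post-treatment", with no visit attached to the word baseline.
- **Statistical Methods of Analysis**: "The primary outcome of effectiveness will be a paired comparison of baseline to all applicable post-baseline time points", using VISIA and SHI data. The formula headed "Percent Mean Change from Baseline" divides by the baseline mean. Neither states which image set is meant.
- **Visit text**: standard, Vectra and VISIA images are ordered at Screening in each Part and again at the treatment visits, with the restriction "This will only be completed before their first treatment". That is a Day 0 pre-laser set in both Parts.
- **Study Timeline and Procedures**: the Part 1 imaging rows are marked at Screening and the two follow-ups only.

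The first primary endpoint is "Quantifying Improvement in overall facial hyperpigmentation in response to laser treatment". The Part 1 pre-treatment regimen includes "4-6 weeks of 4% Hydroquinone cream applied twice daily to entire face" and four weeks of nightly tretinoin. Purpose and Objective requires at least 30 days of the regimen before the treatment series.

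**The concern.** The main efficacy result is a within-subject change from baseline in an uncontrolled study, so the choice of baseline determines what the result measures. In Part 1 the two candidate images lie on either side of a topical run-in. Potential Risks describes hydroquinone as an effective treatment for hyperpigmentation, so the run-in acts on the outcome itself.

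Where the plan names a baseline, it names the image taken before the run-in. Following the SHI text as written would count any lightening before the first laser pass as part of a change that the endpoint attributes to the laser. For VISIA, the other primary measure, the choice is left to whoever does the analysis. The images that would separate the two periods are already ordered by the visit text, but no analysis uses them.

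**Working it through.** The documents give no mean, SD, effect size, power or split of the approximately 20 subjects by Part. There is no stated figure to reproduce, and the bias cannot be estimated. What can be checked is the order of events, the timing, and how the plan's own formula behaves.

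**1. Which image is baseline?**

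| Source | Baseline visit |
|---|---|
| Nikon photographs | Screening |
| SHI (primary endpoint 2) | Screening |
| VISIA (primary endpoint 1) | not stated |
| Statistical Methods of Analysis | not stated |
| Part 1 schedule table | Screening is the only pre-laser imaging mark |
| Visit text, both Parts | images at Screening and at Day 0; neither is called the analysis baseline |

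The confidentiality section also mentions photographs at treatment visits, which agrees with the visit text and not with the table. The table layout may be damaged in the available copy, but as it stands it conflicts with the visit text.

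**2. What lies between the two images in Part 1?** Screening is Day -42 to -28, and prescriptions are sent at that visit. Hydroquinone (4-6 weeks) and tretinoin (4 weeks) follow, then Day 0 imaging, then the first laser treatment. The Screening image therefore precedes the run-in and the Day 0 image follows it.

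**3. Share of the interval before any laser exposure, Part 1.** Share = run-in days / (run-in days + follow-up day), at nominal visit days.

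| Days before Day 0 | To Day 90 | To Day 150 |
|---|---|---|
| 30 (minimum in Purpose and Objective) | 30/120 = 25.0% | 30/180 = 16.7% |
| 42 (early end of Screening window) | 42/132 = 31.8% | 42/192 = 21.9% |
| 28 (late end of Screening window) | 28/118 = 23.7% | 28/178 = 15.7% |

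The 28-day row conflicts with the 30-day minimum and is shown only because the Screening window allows it.

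**4. Effect on the plan's formula (assumed values only).** Percent change = 100 x (visit mean - baseline mean) / baseline mean. Assume a mean SHI of 2.00 at Screening and no further topical effect after Day 0.

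- Run-in effect -10%, laser effect zero: Day 0 = 1.80, follow-up = 1.80. Change is (1.80 - 2.00)/2.00 = -10.0% from Screening and 0.0% from Day 0.
- Run-in effect -10%, laser effect -10%: Day 0 = 1.80, follow-up = 1.62. Change is (1.62 - 2.00)/2.00 = -19.0% from Screening and (1.62 - 1.80)/1.80 = -10.0% from Day 0.

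**5. Effect on the test (assumed values only).** Take a two-sided paired t-test at 0.05, no laser effect, and a run-in effect stated in SDs of the paired difference. The probability of rejecting against Screening, from the noncentral t distribution, is:

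| Run-in effect (SD) | n = 20 | n = 15 |
|---|---|---|
| 0.2 | 0.14 | 0.11 |
| 0.5 | 0.57 | 0.44 |
| 0.8 | 0.92 | 0.82 |

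A run-in effect of moderate size could therefore decide the result. The documents do not say whether there is one.

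**6. Part 2 Screening (a separate, minor point).** The schedule table puts Screening at Day -30 to -1 (30 possible days); the visit text says Day -42 to -28 (15 possible days). They share Days -30 to -28. The washout after Screening is 30 days in Purpose and Objective, 4 weeks in the exclusion criteria and in Subject Instructions (there as a minimum), and 4-6 weeks in the table note. With 30 days, 1 of 30 table days and 13 of 15 visit-text days leave enough room. With 28 days, 3 of 30 and 15 of 15 do.

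**The case against.** The strongest reply is that the plan does have a baseline, namely Screening, and that this is deliberate. The primary objective also covers the adjunctive topical regimen, and secondary endpoint 2 concerns tretinoin and hydroquinone before and after treatment. An image taken after the pre-treatment regimen cannot be the baseline for that regimen. This stands: a Screening baseline is legitimate for the whole package, and the contrast should be kept. It does not answer the first primary endpoint, which is worded as response to laser.

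It is also fair to say that Day 0 does not isolate the laser. Topicals continue in Part 1 to the end of the study, clobetasol and ice are used in Part 2, and there is no control group. Day 0 removes the run-in from the contrast and nothing more.

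Three stronger readings are tempting but not supported:

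- A reader might infer that no baseline is named anywhere. The SHI and Nikon sections both point to Screening; the gap is in the VISIA and statistics sections.
- A reader might infer that Day 0 images could enter the analysis as a post-baseline time point. The primary endpoints refer to post-treatment visits, and the VISIA section lists only the 1-month and 3-month images after baseline. A pre-laser image fits neither.
- A reader might take the time shares as the proportion of the effect that is spurious. They describe the calendar only; the true run-in effect could be nil or large.

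**Conclusion.** The point holds and should be fixed before analysis. Baseline is Screening for SHI and the Nikon photographs, unstated for VISIA and in Statistical Methods of Analysis, and the Day 0 images ordered by the visit text have no stated use. In Part 1 a change from Screening includes any lightening during the run-in, yet the endpoint reads as response to laser.

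The size of the bias is unknown. Between a quarter and a third of the Part 1 interval to Day 90 (25-32%), and about a fifth of that to Day 150 (17-22%), precede laser exposure. This assumes nominal visit days and a run-in of 30 to 42 days. The percent-change and rejection figures rest on invented inputs and show only that the choice can matter.

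For Part 2 the corresponding effect is an inference. If Screening images precede the washout, they may show subjects still on topicals, mainly those continuing from Part 1. The contradictory Part 2 windows and washout lengths must be reconciled whichever baseline is chosen.

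**What to change.** - For VISIA and SHI in each Part, name the Day 0 pre-laser image as baseline for the primary laser-response contrast. Describe that contrast as laser plus concurrent regimen, not laser alone.
- Keep Screening to follow-up as a separately labelled whole-regimen contrast. In Part 1, report Screening to Day 0 as the run-in change relevant to secondary endpoint 2.
- State in advance which contrast is primary for each endpoint. Whether the others carry p-values is for the sponsor to decide.
- Align the schedule table, the Assessments text and the SHI text with the visit text, and report how many subjects lack a Day 0 image.
- Reconcile the two Part 2 Screening windows with each other and with the stated washout lengths.

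The cost is protocol and SAP wording, a corrected table, SHI scoring of the Day 0 images and a few extra summaries. No procedure is added, because the visit text already requires the images. The downside is that some Day 0 images may not exist if the site followed the table, and the Day 0 contrast would then have fewer subjects. That should be checked first.
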